2.1 Primary Objectives

Immunogenicity

Cervarix immunogenicity

- To demonstrate that the humoral immune response (in terms of geometric mean titers [GMTs]) to Cervarix after concomitant administration with the CYD dengue vaccine is non-inferior to the humoral immune response (in terms of GMTs) after sequential administration with the CYD dengue vaccine measured 28 days after the last dose of Cervarix*

CYD dengue vaccine immunogenicity

- To demonstrate that the humoral immune response (in terms of GMTs) to the CYD dengue vaccine after concomitant administration with Cervarix is non-inferior to the humoral immune response (in terms of GMTs) to the CYD dengue vaccine after sequential administration with Cervarix measured 28 days after the last dose of the CYD dengue vaccine*

* Providing that the number of evaluable seropositive subjects allows a global power of at least 80% (otherwise analyses will be descriptive). The endpoints for the primary objectives are presented in [Section 9.1](#).

2.2 Secondary Objectives

Immunogenicity

Cervarix immunogenicity

- To demonstrate that the humoral immune response (in terms of seroconversion) to Cervarix after concomitant administration with the CYD dengue vaccine is non-inferior to the humoral immune response (in terms of seroconversion) to Cervarix sequential administration with the CYD dengue vaccine measured 28 days after the last dose of Cervarix*
- To describe the humoral immune response to Cervarix at baseline and after each dose of Cervarix in each and any group

CYD dengue vaccine immunogenicity

- To describe the humoral immune response to the CYD dengue vaccine at baseline and after each dose of the CYD dengue vaccine, in each and any group

* Providing that the number of evaluable seropositive subjects allows a global power of at least 80% (otherwise analyses will be descriptive).

Safety

Cervarix and CYD dengue vaccine safety

- To describe the safety of Cervarix and CYD dengue vaccine after each and any dose in each group

The endpoints for the secondary objectives are presented in [Section 9.2.1.1](#) and [Section 9.2.2.2](#).

3 Investigators and Trial Organization

This trial will be conducted in approximately 3 centers in Mexico. The Principal Investigators and any sub-investigators at the individual sites will be coordinated by one Coordinating Investigator. Details of the trial centers, the Investigators at each center, and the Coordinating Investigator(s) are provided in the “List of Investigators and Centers Involved in the Trial” document.

Independent Data Monitoring Committee

An IDMC will be involved in the regular review of hospitalized VCD cases, including assessment of severity. Additionally, any related serious adverse event (SAE) or death will be promptly reviewed by the IDMC.

Safety Management Team

An internal safety management team (SMT) will perform a safety analysis on safety data during the conduct of the trial.

Laboratories

Immunogenicity assessments will be performed by Sanofi Pasteur GCI (Swiftwater, Pennsylvania, USA) or outsourced laboratory under the management of GCI.

Sponsor's Responsible Medical Officer

The Sponsor's Responsible Medical Officer (RMO) (the person authorized to sign this protocol and any amendments on behalf of the Sponsor) is [REDACTED], [REDACTED], [REDACTED]
[REDACTED].

4 Independent Ethics Committee / Institutional Review Board

Before the investigational product can be shipped to the investigational site and before the inclusion of the first subject, this protocol, the ICF and AF, subject recruitment procedures, and any other written information to be provided to subjects must be approved by, and / or receive favorable opinion from, the appropriate Independent Ethics Committee (IEC) or Institutional Review Board (IRB).

In accordance with Good Clinical Practice (GCP) and local regulations, each Investigator and / or the Sponsor are responsible for obtaining this approval and / or favorable opinion before the start of the trial. If the protocol is subsequently amended, approval must be re-obtained for each substantial amendment. Copies of these approvals, along with information on the type, version number, and date of document, and the date of approval, must be forwarded by the Investigator to the Sponsor together with the composition of the IEC / IRB (the names and qualifications of the members attending and voting at the meetings).

The Investigator will submit written summaries of the status of the trial to the IEC/IRB annually, or more frequently if requested. All SAEs occurring during the trial that are related to vaccination

will be reported by the Investigator to the IEC/IRB, according to the IEC/IRB policy. The submission to Ministry of Health will be completed by the Sponsor.

5 Investigational Plan

5.1 Description of the Overall Trial Design and Plan

5.1.1 Trial Design

This is a Phase IIIb, randomized, open-label, multicenter study in 480 female subjects aged 9 to 14 years in Mexico.

Subjects have been randomized in a 1:1 ratio into one of the 2 following groups to receive:

- Group 1 (N=240): 3 doses of CYD dengue vaccine and 2 doses of Cervarix (Human Papillomavirus Bivalent [Types 16 and 18] Vaccine, Recombinant; GlaxoSmithKline) concomitantly to the 2 first doses of CYD dengue vaccine
- Group 2 (N=240): 3 doses of CYD dengue vaccine and 2 doses of Cervarix sequentially to the 2 first doses of CYD dengue vaccine

For both vaccines, each dose is to be administered 6 months apart.

As per Protocol Amendment 1, only subjects identified as dengue-exposed (seropositive) before administration of the first CYD dengue injection and who consented to receive the remaining injection of dengue vaccine will continue in the study as per initial study procedures. Subjects identified as unexposed (seronegative) at baseline, will only be able to continue in the study for a 6-month safety follow-up. They will not receive the third and last injection of CYD dengue vaccine.

5.1.2 Justification of the Trial Design

There is currently no data on concomitant administration of CYD dengue vaccine with other vaccines in the indicated population aged 9-45/60 years of age. Based on the current age indication of the CYD dengue vaccine, co-administration data with Cervarix, currently used in public sector school-based vaccination programs in females aged 9 years and above, could support implementation of school-based vaccination programs for CYD vaccine. Therefore, the present CYD71 study will investigate the immunogenicity and safety of the CYD dengue vaccine candidate when it is administered concomitantly or sequentially with Cervarix at least 28 days apart in female subjects aged 9 to 14 years.

5.1.3 Trial Plan

A summary of the schedule of study vaccination and blood samplings for eligible subjects is provided in [Table 5.1](#).

Table 5.1: Injection and blood sampling schedule by Group

Period	Prior to Amendment 1						Post Amendment 1	
Visit (V)	V01	V02	V03	V04	V05	V06	V07	V08
Timing	D0	M1	M2	M6	M7	M8*	M12 or M13*	M13 or M14*
Group 1†	Cervarix + CYD			Cervarix + CYD			CYD	
	BL	BL			BL			BL
Group 2	Cervarix	CYD		Cervarix	CYD		CYD	
	BL	BL	BL		BL	BL		BL
Subjects not receiving the next CYD‡							Safety follow-up (6 months after the last CYD dengue vaccine injection)	

D: day; M: month; BL: blood sample; CYD: CYD dengue vaccine

* In the original protocol v1.0, subjects from Group 1 were expected to attend V07 at M12 and V08 at M13. Likewise, subjects from Group 2 were expected to attend V07 at M13 and V08 at M14.

At the time of Protocol Amendment 1, procedures planned at V07 (most subjects) or V08 (2 subjects from Group 1) were on hold, depending on subjects' progression. Time for the approval of Protocol Amendment 1 by the competent authorities and completion of the associated logistic tasks will result into a delay of study activities (approximately 6 months), and thus to an extension of study duration for dengue exposed subjects.

† When concomitantly administered, the CYD dengue vaccine and Cervarix will be administered in 2 different sites with the CYD dengue vaccine administered in one deltoid and Cervarix in the other deltoid

‡ This includes seronegative subjects that consent to remain in the study and seropositive subjects that consent to stay in the study but prefer not to receive the next dose of CYD dengue vaccine

At the time of Protocol Amendment 1 writing, all subjects from both groups have received the second injection of CYD dengue vaccine and completed the vaccination schedule for Cervarix. Only 2 subjects from Group 1 had completed the 3-dose schedule for the CYD dengue vaccine. Visits on hold were:

- For Group 1, Visit 7 (M12) was on hold for most of the subjects and Visit 8 (M13) was on hold for the 2 subjects who had received the third dose of CYD dengue vaccine.
- For Group 2, Visit 7 (M13).

Dengue unexposed subjects will not receive further dengue vaccine injection. If they consent to continue their participation in the study, they will be contacted by phone call for a safety follow-up 6 months after the last injection. They will not attend any further study visits (except the unscheduled visit and/or the next schedule visit planned to sign the ICF) and will no longer provide blood samples.

Dengue exposed subjects who consent to continue in the study but decided against receiving the last CYD dengue vaccine injection will be contacted by phone call for a safety follow-up 6 months after the last injection. They will not attend any further study visits (except the unscheduled visit and/or the next scheduled visit planned to sign the ICF) and will no longer provide blood samples.

For dengue exposed subjects who consent to continue in the study and to receive the next CYD dengue vaccine injection, procedures will be as followed:

Vaccinations

Subjects will receive 5 injections, 3 doses of CYD dengue vaccine and 2 doses of Cervarix administered either concomitantly (Group 1) or sequentially (Group 2):

- Group 1: Cervarix and CYD dengue vaccine (concomitantly) at Day (D)0 and Month (M)6, and CYD dengue vaccine (alone) at M12
- Group 2: Cervarix (alone) at D0 and M6, and CYD dengue vaccine (alone) at D0+28D (M1), M6+28D (M7), and M12+28D (M13)

Study Visits

Subjects will have to attend 6 (Group 1) or 8 (Group 2) visits and will have 1 phone call for the 6-month follow-up after the last injection of CYD dengue vaccine. Interim phone calls will be given 7 days (+8 days of time windows) after each injection and approximately 2 months after blood samples during the 6-month period between each vaccination.

An unscheduled visit or phone call will take place during the study pause in order to communicate the new data on the CYD dengue vaccine to each subject (delivering or reading of a “Dear ParticipantLetter”). This visit will be before the next visit initially planned (V07 for most subjects; V08 for 2 subjects). Dengue serostatus at baseline may be communicated to the subjects, if available, at the time of the unscheduled visit.

Subject’s participation in the study was expected to be of 18 or 19 months. Time for the approval of Protocol Amendment 1 by the competent authorities and completion of the associated logistic tasks will result in a hold of study activities (approximately 6 months), and thus, in an extension of study duration for dengue exposed subjects.

Blood Samples

Subjects will provide blood samples:

- for CYD dengue vaccine immunogenicity assessments by dengue neutralizing Abs (4 mL) before the first vaccination (at D0 in Group 1, and M1 in Group 2), and 28 days after each vaccination with CYD dengue vaccine (M1, M7 and M13 in Group 1, and M2, M8 and M14 in Group 2)
- for HPV immunogenicity assessments by ELISA (2 mL) before the first vaccination at D0, and 28 days after each vaccination with Cervarix (M1 and M7)

Additional biological samples that may be collected at any time throughout the study period, regardless of the subject’s dengue serostatus:

- for virological confirmation of hospitalized suspected dengue case within the first 5 days after fever onset (or as soon as possible if not within the 5 days) (approximately 3 mL) by NS1 Ag ELISA, and/or wild type (WT) dengue RT-PCR
- in the event of SAEs (including serious AEs of special interest [AESIs])
- to assess AEs that may be indicative of viscerotropic or neurotropic disease (see Guidelines for Assessing Viscerotropic and Neurotropic AE).

Urine samples

All subjects of childbearing potential will provide urine samples for urine pregnancy test before each injection.

A schedule of assessments and study vaccinations is provided in the [table of study procedures](#).

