‡ All subjects will either attend an unscheduled visit (V00) or have an unscheduled phone call (PC00) during the study pause and **before** the next scheduled visit (V07 for most subjects; V08 for 2 subjects). During the unscheduled visit or phone call, the subject will be informed about the new safety data thanks to a “dear participant letter” and on their baseline serostatus result. The signature of the ICF/AF by the parents/subjects and the check of contraindications to continue in the study will be performed at the next visit planned, as applicable.

§ The 6-month phone call will be given to all subjects who consented to continue in the study whether they were identified as “dengue-exposed” or “dengue unexposed”

** A full physical and clinical examination will be performed and documented on each vaccination visit (mandatory before vaccination) and at the Investigator’s discretion if necessary based on the health status of the subject for the other visits.

†† Concomitant therapy will be collected for Days 0–28 after each injection only

‡‡ In female subjects of childbearing potential. Result of urine pregnancy test should be confirmed as negative before vaccination.

§§ Blood samples planned during vaccination visits will be taken before vaccination

*** In such case, 1 unplanned acute blood sample (approximately 3 mL) will be collected for virological confirmation of dengue disease, by NS1 (nonstructural protein 1) antigen test (ELISA), and/or WT dengue RT-PCR

††† Interim phone calls will be given 7 days (+8 days of time window) after each injection (PC1: V01 + 7 days, PC2: V02 + 7 days, PC4: V04 + 7 days, PC5: V05 + 7 days, and PC7: V07 + 7 days) and approximately 2 months after blood samples (PC3: M3 or M4, PC6: M9 or M10, and PC8: M15 or M16) during the 6-month period after each vaccination.

††† MA will be delivered to subjects who will not receive further CYD dengue vaccine injection but consent to continue their participation in the study.

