5.1.4 Visit Procedures

All information collected during the study visits must be reported into the source documents. Some of the following information will also be recorded in the case report form (CRF).

Visit 1 (Day 0): Inclusion, Randomization, and Vaccination

The Investigator or designated study personnel will:

- 1) Give the subject's parent/legally acceptable representative information about the trial, obtain written informed consent (ICF and AF when applicable), and give him/her a signed copy.
- 2) Obtain significant medical history about the subject and history of dengue infection.
- 3) Collect demographic data.
- 4) Check concomitant medications and record every reportable medication ongoing at the time of vaccination.
- 5) Check inclusion and exclusion criteria for eligibility.
- 6) Perform a physical examination and record the subject's axillary temperature.
- 7) For subjects of childbearing potential^a, perform a urine pregnancy test.
- 8) Allocate a subject number to the subject.
- 9) Scratch-off the randomization list to obtain the group allocation, and sign it.
- 10) Obtain the first blood sample^b (see [Section 7.1](#) for detailed instructions regarding the handling of blood samples). Blood is to be taken from the limb opposite to the one that will

^a To be considered of non-child-bearing potential, a female must be pre-menarche, surgically sterile, or using an effective method of contraception or abstinence from at least 4 weeks prior to vaccination and until at least 3 weeks after vaccination.

^b It is important to note that, if the attempt(s) to collect blood is (are) unsuccessful, the subject should be given the opportunity for another attempt, even on another day. If ultimately a blood sample cannot be obtained, the reason will be recorded in the CRF. In that case, and if the subject wants to participate in the trial, she will be vaccinated.

be used for vaccination for sequential injection (Group 2), or from the limb opposite to the one that will be used for CYD dengue vaccine injection for concomitant injection (Group 1).

- 11) Inject the first dose of Cervarix to all subjects (from Groups 1 and 2) and the first dose of CYD dengue vaccine to subjects randomized into Group 1 (for concomitant vaccination, the injections are made in opposite deltoid)
- 12) Keep the subject under observation for 30 minutes, and record any immediate AE in the source document.

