- 13) Record the date of injection(s), the site and side of injection(s) and the route of administration(s), as well as the dose number of the vaccine(s).
- 14) Give the parent/legally acceptable representative a diary card (DC), a thermometer, and a ruler, and go over the instructions for their use.
- 15) Remind the parent/legally acceptable representative to bring back the DC when they return for Visit 2 at a specified date and time.
- 16) Remind the parent/legally acceptable representative to call the study center if a serious medical event occurs.
- 17) Complete the relevant case report form (CRF) pages for this visit.

Phone Call 1 (PC1) (7 days [+8 days] after Visit 1)

All subjects, who received study vaccination(s), will be contacted 7 days after vaccination (+8 days time windows). During this contact, the Investigator or designated study personnel will ask the subject or parent/legally acceptable representative if the subject has experienced any SAE, including hospitalized suspected dengue case, in the time since vaccination. If it did occur, follow the instructions for reporting it. The Investigator or designated study personnel will also remind the instructions to the parent/legally acceptable representative and to complete regularly the DC. A follow-up visit can be arranged depending on the info recorded during the phone call.

Visit 2 (Month 1; 28 [+14] days after Visit 1)

The Investigator or designated study personnel will:

- 1) Check the information entered into the DC by interviewing the subject / subject's parent(s) / legally acceptable representative(s) and request information concerning any medical event, serious or not, that may have occurred since Visit 1.
- 2) Perform a physical examination (Group 2 only) and record the subject's axillary temperature (if necessary).
- 3) Collect information regarding the subject's medication status since the previous visit.
- 4) For subjects of childbearing potential, perform a urine pregnancy test before injection (subjects in Group 2 only).
- 5) Obtain the second blood sample (see [Section 7.1](#) for detailed instructions regarding the handling of blood samples).
- 6) Review temporary and definitive contraindications to vaccination (Group 2 only).

- 7) Inject the first dose of CYD dengue vaccine to subjects randomized into Group 2.
- 8) Keep the subject under observation for 30 minutes, and record any immediate AE in the source document (Group 2).

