- 4) Perform a urine pregnancy test before injection (for woman of childbearing potential only).
- 5) Review temporary and definitive contraindications to vaccination
- 6) Inject the second dose of Cervarix to all subjects (Groups 1 and 2) and the second dose of CYD dengue vaccine to subjects in Group 1 (6 months post-dose 1).
- 7) Keep the subject under observation for 30 minutes, and record any immediate AE in the source document.
- 8) Record the date of injection(s), the site and side of injection(s) and the route of administration(s), as well as the dose number of the vaccine(s).
- 9) Give the parent(s)/legally acceptable representative(s) a DC.
- 10) Remind the parent(s)/legally acceptable representative(s) to bring back the DC when they return for Visit 5 at a specified date and time.
- 11) Complete the relevant CRF pages for this visit.

Phone Call 4 (PC4) (7 [+8 days] days after Visit 4)

The same procedures as those described for PC1 will be followed.

Visit 5 (Month 7; 6 months /± 20 days/ after Visit 2)

The Investigator or designated study personnel will:

- 1) Review the pages of the DC with the parent(s)/legally acceptable representative(s), including any AEs, medications, or therapy that occurred since vaccination.
- 2) Perform a physical examination and record the subject's axillary temperature
- 3) Check concomitant medications and record every reportable medication ongoing at the time of vaccination.
- 4) Obtain the blood sample (see [Section 7.1](#) for detailed instructions regarding the handling of blood samples).
- 5) For female subjects of childbearing potential, perform a urine pregnancy test before injection (subjects in Group 2 only).
- 6) Review temporary and definitive contraindications to vaccination
- 7) Inject the second dose of CYD dengue vaccine to subjects in Group 2 (6 months post dose 1).
- 8) Keep the subject under observation for 30 minutes, and record any immediate AE in the source document (Group 2).
- 9) Record the date of injection, the site and side of injection and the route of administration, as well as the dose number of the vaccine (Group 2).

- 10) Give the parent(s)/legally acceptable representative(s) a DC for Group 2 and Group 1 (for Group 1 DC for SAE collection only).
- 11) Remind the parent(s)/legally acceptable representative(s) of subjects in Group 2 to bring back the DC when they return for Visit 6 at a specified date and time.

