- **Subjects identified as dengue exposed, choosing to receive the last CYD dengue vaccine injection.** The procedures described for Visit 4 will be followed, except that no dose of Cervarix will be injected and CYD dengue vaccine will be injected to all eligible subjects (third and last dose, given 12 months post-injection 1, depending on the duration of the study pause).
- **Subjects identified as dengue exposed, choosing not to receive the last CYD dengue vaccine injection AND subjects identified as dengue unexposed:**
 - a) Give the parent(s)/legally acceptable representative(s) a memory aid (MA).
 - b) Remind the parent(s)/legally acceptable representative(s) to keep the MA available when they will be called for Safety Follow-up Telephone Call at a specified date and time.
 - c) Complete the relevant CRF pages for this visit.
 - d) Complete the termination record of the CRF.

The following visit procedures will only apply to Subjects identified as dengue exposed, choosing to receive the last CYD dengue vaccine injection

Phone Call 7 (PC5) (7 days [+8 days] after Visit 7)

The same procedures as those described for PC1 will be followed.

Visit 8 (Month 13 (Group 1) or Month 14 (Group 2); 28 [+14] days after Visit 7)

The Investigator or designated study personnel will:

- 1) Review the pages of the DC with the parent(s)/legally acceptable representative(s), including any AEs, medications, or therapy that occurred since vaccination.
- 2) Perform a physical examination and record the subject's axillary temperature.
- 3) Check concomitant medications and record every reportable medication ongoing at the time of vaccination.
- 4) Obtain a blood sample (see [Section 7.1](#) for detailed instructions regarding the handling of blood samples).
- 5) Give the parent(s)/legally acceptable representative(s) a memory aid (MA).
- 6) Remind the parent(s)/legally acceptable representative(s) to keep the MA available when they will be called for Safety Follow-up Telephone Call at a specified date and time.
- 7) Complete the relevant CRF pages for this visit.
- 8) Complete the termination record of the CRF.

Phone Call 8 (PC8) (approximately 2 months after Visit 8)

The same procedures as those described for PC1 will be followed.

Safety Follow-up (6-month period after last vaccination) for all subjects, exposed and unexposed, having accepted to continue participation in the trial post-amendment 1

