5.2.5 Exclusion Criteria

An individual fulfilling *any* of the following criteria is to be excluded from trial enrollment:

- 1) Subject is pregnant, or lactating, or of childbearing potential (to be considered of non-childbearing potential, a female must be pre-menarche^a, surgically sterile, or using an effective method of contraception or abstinence from at least 4 weeks prior to the first vaccination and until at least 4 weeks after the last vaccination)
- 2) Participation at the time of study enrollment (or in the 4 weeks preceding the first trial vaccination) or planned participation during the present trial period in another clinical trial investigating a vaccine, drug, medical device, or medical procedure
- 3) Planned receipt of any vaccine in the 4 weeks following any trial vaccination
- 4) Previous vaccination against dengue disease with the trial vaccine
- 5) Previous vaccination against HPV disease with either the trial vaccine or another vaccine
- 6) Receipt of immune globulins, blood or blood-derived products in the past 3 months
- 7) Known or suspected congenital or acquired immunodeficiency (including HIV infection with impaired immune function); or receipt of immunosuppressive therapy, such as anti-cancer chemotherapy or radiation therapy, within the preceding 6 months; or long-term systemic corticosteroid therapy (prednisone or equivalent for more than 2 consecutive weeks within the past 3 months)
- 8) History of HPV infection, confirmed either clinically, serologically, or microbiologically as reported by subject or parent/legally acceptable representative
- 9) Known systemic hypersensitivity to any of the vaccine components, or history of a life-threatening reaction to the vaccines used in the trial or to a vaccine containing any of the same substances^b
- 10) Thrombocytopenia, contraindicating intramuscular vaccination
- 11) Bleeding disorder, or receipt of anticoagulants in the 3 weeks preceding inclusion, contraindicating intramuscular vaccination

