^a For pre-menarche females, the young female patients will declare by themselves (and/or their parent(s) or other legally acceptable representative(s) if they have not yet started menstruation. If a young female patient reaches menarche during the study, then she is to be considered as a woman of childbearing potential from that time forward. Examples of effective methods of contraception include oral contraception (pill), intrauterine device, diaphragm or condoms, contraceptive foam or cream, hormonal implants, transdermal patch, or parenteral contraception

^b The components of CYD dengue vaccine and Cervarix are listed in Section 6.1 and in the Investigator's Brochure

- 12) Deprived of freedom by an administrative or court order, or in an emergency setting, or hospitalized involuntarily
- 13) Current alcohol abuse or drug addiction that, based on Investigator's judgment, may interfere with the subject's ability to comply with trial procedures.
- 14) Chronic illness that, in the opinion of the Investigator, is at a stage where it might interfere with trial conduct or completion
- 15) Identified as an Investigator or employee of the Investigator with direct involvement in the proposed study, or identified as an immediate family member (ie, parent, spouse, natural or adopted child) of the Investigator or employee with direct involvement in the proposed study
- 16) Self-reported Hepatitis B, Hepatitis C infection

Temporary Exclusion Criteria:

A prospective subject must not be included in the study until the following conditions and/or symptoms are resolved:

- 1) Moderate or severe acute illness/infection (according to Investigator judgment) or febrile illness (temperature $\geq 38.0^{\circ}\text{C}$) on the day of first vaccination.
- 2) Receipt of any vaccine in the 4 weeks preceding the first trial vaccination

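### The pregnancy-test rule exempts girls who report contraception or abstinence, so a girl already post-menarche at enrolment can receive live CYD dose 3 untested

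*Protocol*

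**What the plan says.** The trial plan (Protocol 5.1.3) sets the rule: "All subjects of childbearing potential will provide urine samples for urine pregnancy test before each injection". The footnote to the Table of Study Procedures repeats the restriction and adds that the result must be negative: "In female subjects of childbearing potential. Result of urine pregnancy test should be confirmed as negative before vaccination". The test row in that table is marked at V01, V04 and V07 for both groups, and at V02 and V05 for Group 2.

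The restricting term is defined in two places. The footnote attached to the Visit 1 test step (5.1.4) reads: "To be considered of non-child-bearing potential, a female must be pre-menarche, surgically sterile, or using an effective method of contraception or abstinence". Exclusion criterion 1 (5.2.5) bars anyone of childbearing potential and uses the same definition, a girl being outside that class if she is pre-menarche, "surgically sterile, or using an effective method of contraception or abstinence from at least 4 weeks prior to the first vaccination".

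One reclassification rule exists. Footnote a to 5.2.5 says that if a girl "reaches menarche during the study, then she is to be considered as a woman of childbearing potential from that time forward".

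For dose 3, the Visit 7 text for exposed subjects who choose the injection says: "The procedures described for Visit 4 will be followed, except that no dose of Cervarix will be injected". The Visit 4 test step is itself confined to women of childbearing potential.

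**The concern.** One term does two jobs. As an eligibility term it admits post-menarche girls who use contraception or abstinence, by classing them as not of childbearing potential. As a testing term it then removes those same girls from the test. They are the enrolled girls in whom pregnancy is biologically possible and for whom the only safeguard is a declaration.

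The stake is detection of pregnancy before a live attenuated vaccine is given to minors. The definitive contraindication in 5.2.7.2 is worded as pregnancy shown by a positive urine test. In a girl who is exempt from the test, that criterion cannot be met before the injection. When Amendment 1 was written, V07 was still on hold for most subjects, with an added delay of about 6 months, so dose 3 was the dose this wording would still govern.

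**Working it through.** No figure in the plan depends on this point, so the check consists of applying the definition to each instruction.

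**1. Every test instruction carries the restriction.** There are eight: the synopsis (urine sampling), the Table of Study Procedures footnote, Section 5.1.3, Visits 1, 2, 4 and 5 in Section 5.1.4, and Section 7.1.4. Visit 7 has no test step of its own and takes over Visit 4's. The footnote to SAP Table 3.1 repeats the same limit.

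**2. Visit 1.** Eligibility is checked at step 5 and the test is performed at step 7. A girl who passes step 5 is, by criterion 1, not of childbearing potential. The footnote on step 7 uses the same three categories. The set of eligible girls to whom step 7 applies is therefore empty: 0 subjects, by definition.

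**3. Visit 7.** Applying the rules to each kind of girl who could receive dose 3:

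| Status | Class under the protocol | Test required at V07? |
|---|---|---|
| Still pre-menarche | Not of childbearing potential | No |
| Surgically sterile | Not of childbearing potential | No |
| Menarche reached on study | Of childbearing potential (5.2.5, footnote a) | Yes |
| Post-menarche at enrolment, has since stopped contraception or abstinence | Of childbearing potential | Yes |
| Post-menarche at enrolment, still reports contraception or abstinence | Not of childbearing potential | **No** |

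The last row is the gap. Compare it with the third: footnote a states no exception for contraception or abstinence. Of two abstinent, menstruating girls at V07, the one whose menarche came just after enrolment is tested and the one whose menarche came just before is not. No reason for the difference is given.

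**4. Is there a backstop?** The contraindication in 5.2.7.2 is defined through the test. Section 5.2.12 forbids further vaccination once a subject is pregnant, but it acts only on a pregnancy already known. Neither the Visit 4 steps that Visit 7 adopts nor the contraindication list includes an explicit re-check of contraception or abstinence.

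**5. Do the two definitions agree?** Not on duration. The Visit 1 footnote asks for contraception or abstinence until 3 weeks after vaccination; criterion 1 asks for it until 4 weeks after the last vaccination.

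**The case against.** The best counter-argument is that the protocol supports a second reading. Footnote a to 5.2.5 ties the term to menarche alone, Visit 4 and 7.1.4 use similar wording about women of childbearing potential, and the contraception-based footnote is attached only to Visit 1. On that reading every post-menarche girl is tested at V07. The test row marked at each vaccination visit also shows that testing was meant to happen; a reading that leaves nobody to test at V01 can hardly be what the authors intended.

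The point about intent stands. The second reading does not repair the text, though. Footnote a covers only girls whose menarche occurs during the study, and the only definition attached to a test step is the one that exempts contracepting and abstinent girls. At best the protocol says two things and a site may follow either.

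A further argument is that the definition looks forward to weeks after vaccination, so it cannot yet be satisfied when the test is due. The same is true of criterion 1, which has to be judged before the first injection. If a declaration suffices there, it suffices at the test step.

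It is also fair to say that 5.2.12 bars vaccination in a known pregnancy without reference to a urine test, that a full examination is mandatory before each vaccination, and that contraindications are reviewed at V07. This narrows the gap to undetected pregnancy, which is what the urine test is there to find. Finally, detailed site procedures are in Operating Guidelines that are not available here, so actual practice cannot be inferred in either direction.

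**Conclusion.** The concern holds, and the testing rule is wrong as written. Read literally, it reaches none of the girls who meet criterion 1 at V01, and it leaves girls who were post-menarche at enrolment and still report contraception or abstinence untested at every later dose.

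For dose 3 the exposed group is limited to such girls who were also dengue seropositive at baseline and consented to the injection, less any among the 2 Group 1 subjects who had already received it. Its size cannot be derived, because neither document gives menarche status, contraceptive use or the number of seropositive subjects.

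The conclusion assumes that sites apply the stated definition and accept a current declaration of contraception or abstinence. Sites may in fact have tested every menstruating girl, and no omitted test is documented. SAP Section 1 describes dose 3 in the past tense, so the finding concerns the protocol as amended and any later protocol that reuses its wording. It does not bear on the non-inferiority comparisons or any other analysis. It should be fixed on subject-safety grounds.

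**What to change.** Separate the two uses of the term. Keep contraception or abstinence as an eligibility condition in exclusion criterion 1, and delete it from the Visit 1 test footnote. That also removes the 3-week versus 4-week mismatch.

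Then state one testing rule in the synopsis, 5.1.3, 5.1.4 (Visits 1, 2, 4, 5 and 7), 7.1.4 and the Table of Study Procedures footnote: every post-menarche subject who is not surgically sterile must have a negative urine pregnancy test before each injection, whatever contraception or abstinence she reports. Footnote a to 5.2.5 is consistent with this and can stay. The SAP Table 3.1 footnote should be aligned.

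The cost is a wording change, a site letter and some additional urine tests. No visit is added. Over the whole schedule a previously exempt girl would have at most 3 more tests in Group 1 (V01, V04, V07) or 5 more in Group 2 (V01, V02, V04, V05, V07). For a girl awaiting dose 3 when Amendment 1 was written, it is one test, at V07.
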